2.8 Interim analyses

- None

3 Statistical Analyses

3.1 Consort Diagram

The consort diagram for the study is shown below, in Figure 1. This combines original study and CR populations and was generated prior to unblinding.

[figure not shown]

Figure 1. Consort Diagram

3.2 Combining CC-COD+ and CC-COD

All analyses described below were initially planned for the original study but will be conducted for the combined original study and CR population. We will also conduct sensitivity analyses with just the CC-COD population.

3.3 Baseline Characteristics

We will conduct descriptive analyses comparing CC-COD/CC-COD+ and EUC characteristics at baseline using a Chi-squared test for categorical variables and a two sample t-test otherwise. Table 6 provides the demographic characteristics of the study participants at baseline. Table 7 provides all outcomes at baseline and at the 6-month follow-up.

Table 6: Sociodemographics and other covariates at baseline

	Overall	Treatment Assignment	
		CC-COD	EUC
Age, n (%)			
18-30 years			
31-40 years			
41-50 years			
51 years and older			
Sex, n (%)			
Male			
Female			
Gender-neutral sex designation (X)			
Race/Ethnicity, n (%)			
White, Non-Hispanic			
Hispanic			
Other race, Non-Hispanic			
Education, n (%)			
Less than high school diploma			
High school graduate/GED			
Any college/higher-level education			
Marital Status, n (%)			
Never Married			
Married/Partnered			
Divorced/Separated/Widowed			
Prior MOUD, n (%)			
Health system, n (%)			
Health system 1			
...			
Health system 4			

Table 7: Outcomes at baseline and 6-months

	Baseline			6-Months		
	Overall	CC-COD	EUC	Overall	CC-COD	EUC
Primary outcomes						
Buprenorphine access, mean (SD) ¹						
Buprenorphine continuity of care, mean (SD)						
PTSD, n (%)						
PTSD Symptoms, mean (SD)						
MDD, n (%)						
MDD Symptoms, mean (SD)						
Secondary outcomes						
Access to MDD and/or PTSD treatment, n (%)						
Quality of care for MDD, n (%)						
Quality of care for PTSD, n (%)						
MDD remission, n (%)						
MDD response, n (%)						
PTSD remission, n (%)						
PTSD response, n (%)						
Suicidality, n (%)						
Opioid Use Frequency, mean (SD)						
Opioid Overdose Events, n (%)						
Physical Health Functioning, mean (SD)						
Mental Health Functioning, mean (SD)						
Exploratory outcomes						
Drug use frequency, mean (SD)						
Stimulant use frequency, mean (SD)						
Alcohol use, mean (SD)						
Opioid Overdose Risk Behaviors, mean (SD)						
Opioid use severity, mean (SD)						

NOTES: ¹Gray cells indicate outcomes not measured at baseline

3.4 Statistical models

3.4.1 Notation

Table 8 provides notation used to describe the statistical models. We note that the sample size per primary care clinic where not large enough to support the use of fixed effects by clinics in our regression models. Instead, we utilize fixed effects for health systems. When the sample sizes for the smallest health systems prove too small (e.g., less than 30 for continuous

outcomes), we will collapse the smallest health systems together for the purposes of our regression models.

Table 8: Notation used to describe the statistical models.

Notation	Description
X_{ij}	The baseline characteristics of participant i at health system j , including both demographics and other baseline characteristics.
P_{ij}	An indicator of prior MOUD treatment for participant i at health system j .
T_{ij}	The random treatment assignment of participant i at health system j .
y_{ij}	An outcome measure for participant i at health system j .
R_{ij}	An indicator denoting whether participant i at health system j responded to the 6-month follow-up survey.
M_{ij}	A mediator of the outcome-treatment relationship for participant i at health system j .

3.4.2 Overview and General Principles

The primary analyses will be performed for the intention-to-treat population, which consists of all randomized subjects. All individual statistical hypotheses will be tested using two-sided tests, with adjustment for multiple testing using a Bonferroni or Benjamini-Hochberg correction. Primary outcomes will be analyzed at a Type I error rate of 1.25% to control the family-wise error rate at 5% (e.g., so $0.05/4=0.0125$ when using a Bonferroni correction or the first p-value threshold for significance with Benjamini-Hochberg). Similarly, secondary and exploratory outcomes will be analyzed at Type I error rates to control family-wise error rate at 5% within domain. See Table 2 and 3 for definition of secondary outcome domains and our exploratory outcomes.

Outcomes derived from the follow-up surveys are subject to nonresponse, and statistical hypotheses based on these outcomes will be tested using nonresponse weighted models, if necessary. Traditionally, a logistic regression model can be specified predicting response using the demographic characteristics listed in Table , the baseline characteristics listed in Table , and the randomized treatment assignment. The model is given by:

$$\log \left(\frac{\Pr(R_{ij}=1)}{1-\Pr(R_{ij}=1)} \right) = \eta_j + \mathbf{X}_{ij} \boldsymbol{\theta} + \gamma T_{ij} + \rho P_{ij}$$

where η_j represent health system fixed effects. The nonresponse weight for participant i in health system j is given by $w_{ij} = \frac{1}{p_{ij}}$, where $p_{ij} = \Pr(R_{ij} = 1)$. However, we will utilize a nonparametric machine learner to estimate our nonresponse weights to allow for more complex relationships between the predictors variables and the odds of being a responder, thereby producing more high-quality nonresponse weights if they are deemed necessary.

To assess whether there is a need for use of nonresponse weights in our final analyses, we will assess how representative our sample of responders is for each outcome using effect sizes (ES) differences. If most of the ES differences are small (e.g., less than 0.1 or 0.2), we will feel good about the representativeness of our sample of responders to the original baseline sample and not utilize nonresponse weights in our final analyses.

In addition, there is potential for item-level missingness among those who completed the baseline and follow-up surveys. We will perform a descriptive analysis that summarizes this type of missing data. Based on prior studies, we expect such missingness to be isolated to very few subjects, and plan to use a single imputation. For the baseline survey, we will use the following criteria for cleaning up missing data:

- For missing items that are part of a composite measure,
 - a. if the scoring algorithm of the composite measure allows for missingness, we will score the composite using that algorithm
 - b. if the scoring algorithm includes a sum of items, and fewer than 50% of component variables are missing, we will score the composite as a sum of the observed items scaled to account for the missing item(s)
 - c. for all others, we will impute the score using a model that includes the treatment assignment, the health system, and prior MOUD exposure as predictors
- For all other missing items, we will use mean imputation within treatment assignment and health system

For the follow-up survey data cleaning, we plan to perform logical imputation solely for missing items that are part of a composite measure, and we will use a single imputation for composite measures using criteria a. and b. described above.

If the item-level missingness is determined to be more prevalent than anticipated, we will implement a multiple imputation strategy. Five multiply imputed datasets will be generated,

and standard rules for combining multiply imputed datasets with nonresponse weighting will be applied.² Imputations will be generated with sequential predictive mean matching using the R package *mice*.³

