9.4.2 ANALYSIS OF THE PRIMARY ENDPOINT(S)

This protocol provides a summary of the statistical analyses, and the SAP provides additional details.

- Buprenorphine access is a time-to-event outcome and will be compared between arms by fitting a Cox proportional hazard regression model. Specification of the model is available in the SAP.
- Days of cumulative buprenorphine treatment will be compared between arms by fitting a linear regression model. Specification of the model is available in the SAP.
- Depression symptom severity and PTSD symptom severity are ordinal scales and will be analyzed using non-response weighted linear regression models. Additional model details and specification of covariates are provided in the SAP.

The primary analyses will be performed for the intention-to-treat population, which consists of all randomized subjects. Procedures for handling missing data are provided in the SAP.

A union-intersection test will be used to test the overall success of the study that combines the four primary outcomes into a single composite hypothesis. In particular, the null hypothesis is the intersection of the four primary outcome null hypotheses (i.e., all null hypotheses are true), and the alternative is the union of the alternative hypotheses (i.e., at least one alternative hypothesis is true). A Bonferroni or Benjamini-Hochberg correction on the individual hypotheses will be used to control the error rate of this composite test. The four primary hypotheses will be analyzed with a Type I error of 1.25%, which accounts for the multiple primary outcomes using a Bonferroni correction to control the family-wise error rate at 5% ($0.05/4 = 0.0125$).

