9.4.3 ANALYSIS OF THE SECONDARY ENDPOINT(S)

Secondary endpoints will be grouped into domains of conceptually related endpoints, and each will be analyzed adjusting for multiple comparison within domain. Preliminary domains are as follows:

Mental Health

- Access to MDD and/or PTSD treatment
- Quality of care for MDD

- Quality of care for PTSD
- MDD remission
- MDD response
- PTSD remission
- PTSD response
- Active suicidal ideation

Substance Use

- Opioid use frequency
- Opioid overdose events

Overall Health

- Physical health functioning
- Mental health functioning

Secondary endpoints will be analyzed using similar approaches as described for the primary endpoints. Additional model details are provided in the SAP. Other statistical issues, e.g. loss to follow up and missing data, will be accounted for using the same techniques as with the primary outcomes.

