2.5 Definitions of outcomes

2.5.1 Primary outcomes

Table 1 defines the primary outcomes of this study. The hypotheses associated with these outcomes are as follows:

1. We hypothesize that patients with a new OUD episode of care who are randomized to CC-COD/CC-COD+ will receive buprenorphine within fewer days after that care episode

than new OUD patients who are randomized to enhanced usual care. Alternatively, the null hypothesis is that there will be no difference in the number of days until receipt of buprenorphine with a new OUD episode of care.

2. We hypothesize that patients who are randomized to CC-COD/CC-COD+ will have more days of buprenorphine treatment within 180 days of study enrollment than patients who are randomized to enhanced usual care. Alternatively, the null hypothesis is that there will be no difference in the number of days of cumulative buprenorphine treatment within 180 days of study enrollment.
3. We hypothesize that, among patients with probable depression at study enrollment, those who are randomized to CC-COD/CC-COD+ will have a greater reduction in depression symptoms 6 months after study enrollment compared to those who are randomized to enhanced usual care. Alternatively, the null hypothesis is that there will be no difference in depression symptoms 6 months after study enrollment among those with probable depression at enrollment.
4. We hypothesize that, among patients with probable PTSD at study enrollment, those who are randomized to CC-COD/CC-COD+ will have a greater reduction in PTSD symptoms 6 months after study enrollment compared to those who are randomized to enhanced usual care. Alternatively, the null hypothesis is that there will be no difference in PTSD symptoms 6 months after study enrollment among those with probable PTSD at enrollment.

A union-intersection test will be used to test the overall success of the study that combines the four primary outcomes into a single composite hypothesis. In particular, the null hypothesis is the intersection of the four primary outcome null hypotheses (i.e., all null hypotheses are true), and the alternative is the union of the alternative hypotheses (i.e., at least one alternative hypothesis is true). As described in subsequent sections, either a Bonferroni or Benjamini-Hochberg correction on the individual hypotheses will be used to control the error rate of this composite test.

Table 1: Definition of primary outcomes

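### SAP 3.4.2 permits Benjamini-Hochberg for individual hypotheses under a 5% family-wise label, which that procedure does not guarantee when some but not all null hypotheses are false

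*SAP*

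**What the plan says.** SAP 3.4.2 sets the general rule: "All individual statistical hypotheses will be tested using two-sided tests, with adjustment for multiple testing using a Bonferroni or Benjamini-Hochberg correction". The next sentence says: "Primary outcomes will be analyzed at a Type I error rate of 1.25% to control the family-wise error rate at 5" per cent. Its parenthesis explains 0.0125 either as the Bonferroni level (0.05/4) or as "the first p-value threshold for significance with Benjamini-Hochberg". It continues that "secondary and exploratory outcomes will be analyzed at Type I error rates to control family-wise error rate at 5% within domain".

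The other places that bear on the choice are:

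- **Primaries, protocol 9.4.2:** "A Bonferroni or Benjamini-Hochberg correction on the individual hypotheses will be used to control the error rate of this composite test". The sentence after it is specific: "The four primary hypotheses will be analyzed with a Type I error of 1.25%, which accounts for the multiple primary outcomes using a Bonferroni" correction.
- **Primaries, SAP 2.5.1:** "either a Bonferroni or Benjamini-Hochberg correction on the individual hypotheses will be used to control the error rate of this composite test".
- **Power, SAP 3.5:** computed at 1.25%, attributed to Bonferroni.
- **Secondaries:** protocol 9.4.3 says "each will be analyzed adjusting for multiple comparison within domain" and names no method. SAP 3.5.2 names Bonferroni.
- **Exploratory outcomes** (SAP section numbered 3.4.3, placed after 3.5.2): Bonferroni or BH.

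No section says how the choice between the two would be made. SAP 2.2 states that the plan was settled in full before unblinding.

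**The concern.** The SAP attaches one error guarantee to two procedures, and only one of them delivers it. For four tests at 5%, the BH thresholds for the ordered p-values are 0.0125, 0.025, 0.0375 and 0.05. The 1.25% in SAP 3.4.2 is therefore the level for every primary under Bonferroni, but only the first step under BH. Once one or two outcomes are clearly positive, a true null can be rejected at a p-value well above 0.0125.

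Four separate primary hypotheses are stated, and SAP Table 11 reports each primary outcome on its own line. The rule therefore decides which endpoints may be called significant. Under BH those individual claims would be reported with a 5% family-wise rate that they may not have.

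**Working it through.** **1. The plan's own figures.** 0.05/4 = 0.0125. With four independent true nulls, 1 − (1 − 0.0125)^4 = 4.91%, so Bonferroni holds 5%; it does so under any dependence.

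The power section can be checked at that level. With 1:1 allocation, the detectable difference is (2.498 + 0.842) × SD × 2/√N:

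- Continuity of care: SD 54.1, N 392 gives 18.25 days (SAP 3.5.1: 18.3).
- PHQ: SD 6.6, N 405 gives 2.19 points (SAP: 2.2).
- PCL-5: SD 17.8, N 368 gives 6.20 points (SAP: 6.23).

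The stated power is thus at the Bonferroni level.

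**2. BH, closed form.** Take four independent tests, two real effects that are certain to be rejected, and two true nulls. The real effects take ranks 1 and 2, so the nulls face 0.0375 and 0.05. At least one null is rejected if either p-value is at or below 0.0375, or if both lie between 0.0375 and 0.05:

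1 − (1 − 0.0375)² + 0.0125² = 0.0736 + 0.0002 = 7.4%.

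The same reasoning gives 7.4% with one near-certain effect and 5.0% with three.

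**3. BH at realistic power.** The documents give neither correlations nor true effects, so these are assumptions: four two-sided normal tests with equal pairwise correlation, and every real effect having the same power at 0.0125. The table shows simulated family-wise error, meaning the chance of rejecting at least one true null, as the maximum over zero to three real effects.

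| Common correlation | 80% power | 50% power |
|---|---|---|
| 0 | 6.9% | 5.9% |
| 0.3 | 6.5% | 5.7% |
| 0.5 | 5.9% | 5.2% |
| 0.6 | 5.5% | 5.0% |
| 0.7 | about 5.0% | below 5% |

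These are maxima, reached with one or two real effects. With three real effects at 80% power, BH gives at most 4.7%. If the two buprenorphine outcomes and the two symptom outcomes form correlated pairs (0.5 to 0.7 within pairs, 0 to 0.2 between), the maximum at 80% power is 6.2% to 6.6%. Holm stayed at or below 5% throughout.

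**4. Composite test.** With all four nulls true, BH rejects at least one in 5.0% of trials at correlation 0 and 4.4% at 0.6.

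**5. What BH adds.** At 80% power and correlation 0, BH makes a false primary claim that Bonferroni would not in 3.4%, 4.4% and 3.4% of trials with one, two and three real effects. It also adds a correct claim in 0.5%, 11.1% and 24.3%.

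**6. BH for the composite test only.** Suppose the p-values are 0.020, 0.024, 0.5 and 0.6. BH rejects two hypotheses, because 0.024 ≤ 0.025. Bonferroni rejects none. Overall success would be declared with no significant primary. At 50% power this happens in up to 2.4% of trials (all four effects real, correlation 0.6).

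**7. Exploratory outcomes.** For five tests at 80% power, the BH maximum is 8.1% at correlation 0, falling to 6.1% at 0.6.

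**The case against.** The strongest reply is that Bonferroni is already the working rule. Protocol 9.4.2 states it for the four primary hypotheses and ties its BH option to the composite test, as SAP 2.5.1 does. SAP 3.5 uses it for power and SAP 3.5.2 for secondaries. In SAP 3.4.2 itself, BH also enters through an illustrative parenthesis after a flat 1.25%.

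Much of this stands, and it rules out some stronger readings:

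- A reader might infer that the primary rule is undefined in both documents. The Bonferroni sentence in protocol 9.4.2 does not support that.
- A reader might infer that SAP 3.4.2 and 3.5.2 contradict each other on secondaries. A general section that offers two methods and a specific section that picks one can be read together.
- A reader might infer that the overall success test is inflated. It was not in any non-negative correlation case run. Negative correlation was not examined for that test.
- A reader might infer that a late choice between the methods adds error beyond BH. It cannot, because BH rejects everything Bonferroni rejects.

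The reply does not remove the point. Protocol 9.1 sends the reader to the SAP for details, and the first sentence of SAP 3.4.2 allows BH for individual hypotheses without limiting it to the composite test.

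**Conclusion.** The concern holds in a bounded form. SAP 3.4.2 permits BH for individual claims under a 5% family-wise label that BH does not guarantee.

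For the four primaries, the excess over 5% is at most about 1.9 percentage points at 80% power and 2.4 points with independent tests and near-certain effects. It disappears at a common correlation of about 0.7 when power is 80%, at about 0.6 when power is 50%, and whenever three effects are real. These sizes depend on assumed equal correlations and equal power, because the plan states neither. That BH lacks the stated guarantee does not depend on them.

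For exploratory outcomes the defect is only the label. This should be fixed, but it does not undermine the composite test or the power calculations.

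**What to change.** Before unblinding:

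- **Primaries:** delete the BH option from SAP 3.4.2, SAP 2.5.1 and protocol 9.4.2. Use one family-wise method for both the composite test and the individual primary claims, so that overall success always comes with at least one significant primary. Bonferroni is the smallest change, since protocol 9.4.2, SAP 3.5 and SAP 3.5.2 already use it. Holm is acceptable if protocol 9.4.2 and SAP 3.5.2 are aligned with it: it has the same first threshold of 0.0125 and is never less powerful than Bonferroni.
- **Secondaries:** keep Bonferroni as in SAP 3.5.2, and name it in protocol 9.4.3.
- **Exploratory outcomes:** use the same method, or restate the goal as false-discovery-rate control in SAP 3.4.2 and the exploratory section.
- **If the blind is already broken:** use Bonferroni as stated in protocol 9.4.2.

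The cost is wording only, with no new power calculation under Bonferroni. The extra rejections that BH would allow, many of them correct, are given up. With two real effects at 80% Bonferroni power and correlation 0, average power per real effect is 80.0% with Bonferroni, 82.3% with Holm and 85.8% with BH.

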2.5.2 Secondary outcomes

There are 13 pre-specified secondary outcomes, which are described in

Table 2. After drafting of the initial SAP, but prior to analyzing outcomes and breaking the blind, some secondary outcomes were modified, cut, or reclassified as exploratory, as detailed in the revision table in section 1.2.

Table 2: Definition of secondary outcomes

Outcome	Population ^b	Definition	Measure Scale	Source
Mental Health				
Access to MDD and/or PTSD treatment	Study participants who did not have any visits (behavioral health treatment or medication) for MDD and/or PTSD in 30 days prior to study enrollment	Receipt of medication and/or behavioral treatment associated with an MDD or PTSD diagnosis within 30 days of study enrollment (initial) or within 180 days of study enrollment (any)	Binary	EMR, Survey
Quality of care for MDD	Study participants with probable MDD at baseline (PHQ-8 ≥ 10) and a new episode of MDD care (no MDD care for at least 30 days prior to enrollment)	Four psychotherapy visits in the first six months or an adequate (60 day) medication trial for new episodes of MDD care (completed within 6 months)	Binary	EMR, Survey
Quality of care for PTSD	Study participants with probable PTSD at baseline (PC-PTSD-5 ≥ 3) and a new episode of PTSD care (no PTSD care for at least 30 days prior to enrollment)	Four psychotherapy visits in the first six months or an adequate (60 days) medication trial for new episodes of PTSD care (completed within 6 months)	Binary	EMR, Survey
MDD remission	Study participants with probable MDD at baseline (PHQ-8 ≥ 10)	PHQ-9 < 5 at 6 months	Binary, based on sum of items (0-27)	Survey
MDD response	Study participants with probable MDD at baseline (PHQ-8 ≥ 10)	PHQ-9 score at 6 months less than 50% of baseline score	Binary, based on sum of items (0-27)	Survey

PTSD remission	Study participants with probable PTSD at baseline (PC-PTSD-5 \geq 3)	PCL-5 < 34 at 6 months	Binary, based on sum of items (0-80)	Survey
PTSD response	Study participants with probable PTSD at baseline (PC-PTSD-5 \geq 3)	PCL-5 score at 6 months less than 50% of baseline score	Binary, based on sum of items (0-80)	Survey
Active suicidal ideation	All study participants	Dichotomized Columbia Suicide Severity Rating Scale at 6 months: answer YES to Question 3, 4, and/or 5 and/or YES to Question 7	Binary	Survey
Substance Use				

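### Two of the SAP's rules for missing baseline survey data use the randomised arm; this makes the baseline tests slightly too liberal and can be removed at no cost

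*SAP*

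**What the plan says.** SAP section 3.4.2 expects little item-level missingness: "we expect such missingness to be isolated to very few subjects, and plan to use a single imputation". It then sets out an ordered list for the baseline survey.

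- Rule a, composites: "if the scoring algorithm of the composite measure allows for missingness, we will score the composite using that algorithm".
- Rule b, sum scores: if "fewer than 50% of component variables are missing, we will score the composite as a sum of the observed items scaled" up for the gaps.
- Rule c, remaining composites: "we will impute the score using a model that includes the treatment assignment, the health system, and prior MOUD exposure as predictors".
- Non-composite items: "we will use mean imputation within treatment assignment and health system".

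Rules a and b use only the participant's own answers. Rule c and the last rule use the randomised arm. For the follow-up survey, "we will use a single imputation for composite measures using criteria a. and b. described above", so arm plays no part there. If item-level missingness proves heavier than expected, the SAP moves to five multiply imputed datasets. It gives no threshold for that move and does not list the predictors.

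SAP section 2.7 places the baseline assessment before randomisation. Section 3.3 compares the arms at baseline with chi-squared and t-tests. Among the secondary outcomes, MDD response is "PHQ-9 score at 6 months less than 50% of baseline score", and PTSD response is built the same way on the PCL-5.

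**The concern.** A value fixed before allocation cannot depend on allocation. In a randomised trial, the difference between arm means at baseline is chance. If the gaps in each arm are filled with that arm's own mean or prediction, the chance difference is carried into the filled values, which are then counted as real observations. Two things follow. The baseline comparison looks more precise than it is. And the filled values are no longer independent of treatment, a property that later analyses take for granted.

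The filled values can travel to:

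- the baseline tests in SAP 3.3;
- the nonresponse weights in 3.4.2, if weights are used;
- the survey-based moderators in 3.4.6;
- the baseline covariates in the mediation models in 3.4.7;
- the two response endpoints, but only through rule c, because PHQ-9 and PCL-5 are composites.

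**Working it through.** No figure in the plan is in dispute, so there is none to reproduce. The check is of reach and size. The documents give no missingness rate; the rates below are assumptions.

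**1. Baseline tests (SAP 3.3).** Take n participants per arm, standard deviation σ and a share m missing at random in each arm.

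- *Arm-mean fill.* The difference in means equals the complete-case difference, with true variance 2σ²/(n(1−m)). The t-test sees n values per arm whose sample variance has shrunk to about σ²(1−m), so it reports 2σ²(1−m)/n. The reported standard error is (1−m) times the true one. The size of a nominal 5% test is therefore 2[1−Φ(1.96(1−m))].
- *Arm-blind fill.* The difference in means shrinks by (1−m), so its true variance is (1−m)²·2σ²/(n(1−m)) = 2σ²(1−m)/n. That is what the test reports, so the size stays at 5%.

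| m | 1.96(1−m) | Size, arm-mean fill |
|---|---|---|
| 1% | 1.940 | 5.2% |
| 5% | 1.862 | 6.3% |
| 10% | 1.764 | 7.8% |

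Simulation agrees. At 0.8%, 5% and 10% missing, the size was 5.2%, 6.0% and 7.9% with the arm-mean fill, and 5.0%, 5.0% and 4.9% with the arm-blind fill. The formula uses one mean per arm. Filling within arm and health system works by the same mechanism, so the figures are approximate for the SAP's rule.

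**2. Response endpoints, through rule c.** SAP Table 9 gives N=368 for PTSD remission, which needs no baseline PCL-5, and N=365 for PTSD response, which does. That suggests 368 − 365 = 3 people (3/368 = 0.8%) without a usable baseline score. For MDD both figures are 405, which suggests none. If all 3 were in one arm of 368/2 = 184 and all changed response status, the PTSD response difference would move by at most 3/184 = 1.6 percentage points. The stated detectable effect is 17.7 points.

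A simulation with no treatment effect assumed baseline PCL-5 mean 45, SD 16, correlation 0.5 with follow-up, missingness unrelated to arm, and 6,000 runs. The nominal level was 0.05/8 = 0.00625, for the eight outcomes in the mental health domain.

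| Missing | Type I error, by arm | Type I error, arm-blind |
|---|---|---|
| 0.8% | 0.0080 | 0.0057 |
| 5% | 0.0055 | 0.0080 |
| 10% | 0.0065 | 0.0057 |

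The Monte Carlo standard error is √(0.00625×0.99375/6000), about 0.001. There is no pattern by method or missingness, and the mean risk difference stayed within about 0.15 points of zero.

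**3. Moderators and baseline covariates.** A linear model with N=405 was run 5,000 times at nominal 5%, with 1%, 5% and 10% missing.

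- The moderator-by-arm test had size 5.1%, 4.7% and 4.6% with fill by arm, and 4.8%, 4.9% and 4.3% arm-blind.
- The treatment test adjusted for the filled covariate had size 5.8%, 5.0% and 4.9% by arm, and 4.7%, 4.9% and 5.0% arm-blind. The 5.8% at 1% missing is high for a Monte Carlo standard error of about 0.3 points. It does not recur at 5% or 10% missing, where a real effect would be larger, so I read it as noise.

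**4. Primary models.** SAP 3.4.4 and 3.4.5 include only health system, prior MOUD exposure and arm. No baseline score enters. Filled values can reach the primary PHQ-9 and PCL-5 analyses only through nonresponse weights, and these are used only if responders differ enough from the baseline sample.

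**The case against.** The case for leaving the rule alone is that almost nothing depends on it. Rules a and b come first and settle most composite gaps without arm. Rule c acts on a sum score only when at least half of its items are blank. For a PHQ-9 completed within three days of screening, items 1 to 8 come from the screener (Protocol 8.1), so rule b covers a missing item 9. The baseline tests are descriptive and decide no endpoint. Single imputation is meant for light missingness, and multiple imputation is the stated fallback. All of this stands, and it is why the point is minor. It does not justify having arm in the two rules, where it adds no information.

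A reader might infer more than the documents support:

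- *That treatment effects are biased.* With missingness unrelated to arm, the expected baseline difference is zero. What is copied is noise, and the simulations show neither bias nor inflated error for response.
- *That the mediators are affected.* They are 3-month measures (SAP 3.4.7) handled by rules a and b. Only the baseline covariates in those models are exposed.
- *That every moderator is affected.* The number of care coordinator visits comes from the registry, not the baseline survey.
- *That blinding is broken.* SAP 2.2 keeps research staff blind until database lock, and filling by arm needs the allocation. But the SAP does not say that the fill is done before lock.

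**Conclusion.** The rule is wrong in principle and small in effect. Its demonstrable consequence is that the section 3.3 baseline tests are too liberal: about 5.2%, 6.3% and 7.8% instead of 5% at 1%, 5% and 10% missing. It also makes arm-dependent the filled baseline values used in any nonresponse weights, the survey-based moderators, the mediation covariates and, through rule c alone, the two response endpoints. No systematic bias was found there, and no clear inflation of type I error.

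This rests on assumed missingness rates, on missingness unrelated to arm, and on reading the 368 and 365 in Table 9 as three missing baseline PCL-5 scores. That reading is uncertain: rule c as written would have filled those scores, so Table 9 may count people before imputation. The multiple-imputation fallback is a separate matter, since using arm in a joint imputation that includes outcomes is not this defect. Lowest severity: a free improvement.

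**What to change.** Delete treatment assignment from both baseline rules in SAP 3.4.2. Rule c would then use health system and prior MOUD exposure. Non-composite items would take the mean within health system, with small systems collapsed as section 3.4.1 already allows. Prior MOUD need not be added to the mean-imputation cells, which could become sparse. Follow-up rules a and b need no change. It would also help to state whether N=365 in Table 9 is before or after imputation.

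The cost is two short deletions. No new data or sample size is needed, and no statistical loss was identified. As a side benefit, arm-free rules can be run and checked while the team is still blind.
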